	
(squamous vs non-squamous), Stage (III vs IV), PD-L1 status, and treatment administered (Chemo-Immuno vs immuno-alone vs others IO combinations) will be considered.
 
AI analysis plan
 
After Ethical approval in each Cancer Center, the third part of the study will start at month 3 and will continue up to 36 months. These periods will allow sufficient time for prospective enrolment and follow-up of patients for at least for 18 months. At month 30, an intermediate version of the P-Model will be released after the collection of the first batch (~100) of patients including multi-OMICs data. At months 54, after the predictive models are build using all the data from 200 patients, the final P-Model will allow to verify if: (i) new predictive system using multi-OMICs results perform better compared to current ones (e.g., PD-L1 or other state of the art biomarkers), (ii) if the model using -omics data perform better compared to the R model, (iii) if there is any specific -omics analysis which perform better compare to other -omics, which would give more value to the model (iv) if the P-Model perform better compared to current biomarker, and compare to the R-model when applied to specific subgroups of patients (e.g., non-squamous vs squamous patients). We will consider this phase successful if the new P-models outperforms current biomarkers prediction at least for 10% in terms of correct prediction of either 2-year PFS and 2-year OS, measured with Harrel's C statistic.

	
The study is conducted in accordance with the Declaration of Helsinki Ethical Principles and Good Clinical Practices and was approved at each site by an independent local ethics committee.
 
During the clinical visit, after receiving adequate study information, the patient may sign an informed consent form, in accordance with the provisions of the local ethical regulations. The consent of the patient must be signed and personally dated by the patient and by the investigator/person designated to conduct the informed consent discussion. The signed and dated declaration of informed consent will remain at the researcher site and must be safely archived by the investigator so that the forms can be retrieved at any time for monitoring, auditing and inspection purposes. A copy of the signed and dated information and consent should be provided to the patient prior to participation.

Ethical considerations and Informed Consent	
In the retrospective part of the study, in case it is not possible to ask and obtain for the informed consent (due to death or inability to reach the patients), to process the patient data and samples, for ethical-administrative reasons, the study falls within the scope and purposes specified by the Regulation (EU) 2016/679 of the European Parliament and of the Council of 27 April 2016 on the protection of natural persons with regard to the processing of personal data and on the free movement of such data, and repealing Directive 95/46/EC (General Data Protection Regulation), in its article 89.1.
 
All clinical centers will be involved in the retrospective phase, while in the prospective phase only 5 out 6 centers will participate (INT, GHD, VHIO, MH and SZMC). The study will involve exporting of CT and PET images from both retrospective and prospective studies from EU cancer centers and US to Israel, while clinical data will be exported from all the EU cancer centers and Israel to US for AI analyses. Biological samples (tissue, blood and stool samples) will be collected from SZMC (Israel) and will be imported in EU countries (Italy, Germany, Spain) for pathology, genomic, circulating and microbiome analyses.

References	
1. Globocan (2018) Available from http://globocan.iarc.fr/Default.aspx (Accessed on 25-Nov-2020).

 
— Sistema Socio Sanitario Regione Lombardia
		OBSERVATIONAL STUDY PROTOCOL	MOD-PRO-G-03- DSC-10
---	---	---	---------------------------------

2. Howlader N, et al. SEER Cancer Statistics Review, 1975–2012. National Cancer Institute, 2015 [resource on the Internet]. Available from: http://seer.cancer.gov/csr/1975_2012/.
3. Sulpher JA, et al. Factors influencing a specific pathologic diagnosis of non-small-cell lung carcinoma. *Clin Lung Cancer*. 2013 May;14(3):238-44.
4. Siegel RL, et al. Cancer Statistics, 2017. *CA Cancer J Clin* 2017; 67:7–30.
5. Lynch TJ, et al. Activating mutations in the epidermal growth factor receptor underlying responsiveness of non-small-cell lung cancer to gefitinib. *N Engl J Med* 2004; 350: 2129-39.
6. Rosell R, et al. Screening for epidermal growth factor receptor mutations in lung cancer. *N Engl J Med* 2009; 361: 958-67.

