The retrospective part of the I³LUNG project includes the analysis of a multicentric retrospective cohort of more than 2,000 patients. This cohort will be used to perform a preliminary knowledge extraction phase and to build a retrospective predictive model for IO (R-Model), that will be used in the prospective study phase to create a first version of the Physician Decision Support System (PDSS) tool, an AI-based tool to provide an easy and ready-to-use access to predictive models, increasing care appropriateness, reducing the negative impacts of prolonged and toxic treatments on wellbeing and

	
healthcare costs. Also, CT and PET scans will be collected and a first radiomic signature will be created to feed the R-Model.
 
The prospective part of the project includes the collection and the analysis of multi-OMICs data from a multicentric prospective cohort of about 200 patients. This cohort will be used to validate the results obtained from the retrospective model through the creation of a new model (P-Model), which will be used to create the final Physician Decision Support System (PDSS) tool.

	
Overall Primary Objective

	
 • Prediction of response to immune checkpoint inhibitors in NSCLC by using clinical, biological, metabolomics, genomics, pathomics and radiomics data.
	
Secondary Objectives

	
 • Prediction of Progression-free survival (PFS) in response to immune checkpoint inhibitors in NSCLC by using clinical, biological, metabolomics, genomics, circulomics, pathomics, microbiome and radiomics data.
	
 • Prediction of Objective Response Rate (ORR) in response to immune checkpoint inhibitors in NSCLC by using clinical, biological, metabolomics, genomics, circulomics, pathomics, microbiome and radiomics data.
	
 • Prediction of Overall survival (OS) in response to immune checkpoint inhibitors in NSCLC by using clinical, biological, metabolomics, genomics, circulomics, pathomics, microbiome and radiomics data.
	
Exploratory Objectives

	
 • Added value of PET/CT into the prediction model for the Primary and Secondary Objectives.
	
 • Prediction of adverse events to immune checkpoint inhibitors in NSCLC by using clinical, biological, genomics, pathomics and radiomics data.

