	
Evaluate the addition of sarcopenia analysis into the prediction model to the response of immune checkpoint inhibitors in NSCLC

	
Specific Objectives:

	
Retrospective Study Phase

	
The primary objective of the retrospective clinical study within the I3LUNG project is to create a model that will be used in the prospective phase to compare the predictive accuracy of ML methods (created using multi-OMICs analyses) with current validated biomarkers (e.g., PD-L1 or available scores). All available jeopardized data of 2000 aNSCLC patients treated at any point with any IO-based therapy will be collected in the first 18 months of the I3LUNG project, including all the data and radiomics detailed in the "Scientific Clinical Study Design" section. This model will be used to create a first version of the Physician Decision Support System (PDSS) tool.

	
Prospective Study Phase

	
The primary objective of the prospective phases to compare the predictive accuracy of ML methods (created using multi-OMICs analyses) to current validated biomarkers (e.g., PD-L1). In this prospective part of the study, multi-OMICs data (pathology, genomics, transcriptomics, metabolomics, circulating immune profiling, microRNA signature classifier, liquid biopsy, microbiome) of 200 patients recruited by 5 cancer centers from the Consortium (INT, GHD, VHIQ,

MH and SZMC) will be collected and then integrated in the platform and used to feed the AI models learned on retrospective data, previously collected in the retrospective study phase.

Other objectives of the prospective phase in particular will include:

1. Integrate both retrospective and prospective data to improve and refine the predictive capabilities of the AI models compared to existing models;
2. Integrate radiomics signature originating from both Computed Tomography (CT) and Positron Emission Tomography–CT (PET-CT) images of the prospective cohort to refine and validate the retrospective radiomics signature;

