Study Endpoints	
Primary endpoint
 
 The predictive model will be developed through artificial intelligence and machine learning analysis of the integrated clinical, biological, genomics, metabolomics, circulomics, pathomics, microbiome and radiomics data. 
Secondary endpoints
 
 Using the predictive model index as classificatory biomarker in Progression-free survival (PFS), defined as the time interval from the date of the first dose of the study treatment until the first date at which disease progression is objectively documented, or death due to any cause, whichever occurs first and calculated through censored Kaplan-Meier analysis. Prediction of Objective response rate (ORR) classification through the predictive model and compared to the assessed by the investigator and defined as the proportion of the participants with confirmed complete response (CR) or partial response (PR) according to Response Evaluation Criteria in Solid tumors (RECIST) v1.1, after initiation of immune checkpoint inhibitors treatment. Using the predictive model index as classificatory biomarker in Overall survival (OS) calculated from diagnosis to death or last follow-up through censored Kaplan-Meier analysis. 
Exploratory endpoints
 
 If available PET/CT will be added to the prediction model and the increment in the prediction performance will be analyzed for the primary and secondary endpoints and the adverse events categories. Machine learning algorithm will be used to predict adverse events categories in response to immune checkpoint inhibitors treatment through the integration of the clinical, biological, genomic, pathomics and radiomics. 
Sarcopenia will be calculated through radiomics by measuring the fat and muscular mass on L1 slice of the chest CT scan and added to the prediction model for the Primary and Secondary Objectives.

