	Cytokines and MicroRNA signature (MSC test)		✓
	Cell free DNA and ctDNA sequencing		✓

 
— Sistema Socio Sanitario Regione Lombardia
		OBSERVATIONAL STUDY PROTOCOL	MOD-PRO-G-03- DSC-10
---	---	---	---------------------------------

Genomics analysis: tumor mutational burden (TMB), somatic copy number alterations, whole genome sequencing, immune infiltration transcriptomic profile		✓
Metabolomics and Microbiome		✓

The clinical/synthetic data will be collected within i3LUNG web-based platform. To each patient will be assigned a code. The CRF form will be filled in from each center with a dedicated account and all these workflows will be addressed using the Data Management Plan.

In particular, for the prospective phase the following multi-OMICs data will be collected for all 200 patients with available tissue and blood. For details see Table 2.

Omics type	Collection	Analyses
Tissue-based (Tasks 3.2, 3.3, 3.4)	Formalin-Fixed Paraffin Embedded (FFPE) tissue blocks from NSCLC patients who underwent surgery or large biopsy will be collected. Every 5 collected samples, FFPE blocks will be shipped to GHD. GHD will then extract samples for immune profiling/TME and will prepare 4 total cores, 2 for genomic profiling and 2 for metabolomics.	
 TME and Tissue Immune Profiling - Reference tissue spots with known expression of the target proteins will be added to each microenvironment Tissue Microarrays (ME-TMA) Genomic profiling (DNA and RNA extraction) and transcriptomics profiling. Metabolomics, metabolite extraction for targeted and untargeted metabolomics analysis

Commentato [CP1]: [name] please check the tubes of WB.

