Sample size and statistical analysis and AI analysis plan	
For the retrospective phase, we have planned to enroll patients based on a first check availability of already treated patients with IO-based therapy among centres.
 
The primary objective of the study is to compare the predictive accuracy of ML methods (created using multi-OMICs analyses) with current validated biomarkers (e.g., PD-L1 or available scores, see Table 2). Considering the number of 200 prospective cases, the study will have at least 85% power to detect a 0.1 increase in predictive accuracy as measured by the area under the ROC curve (AUC), assuming an AUC for validated biomarker alone of at least 0.6, using a one-sided z-test at a significance level of 0,050. The data are assumed to be discrete (rating scale) responses. Stratification Factors: Country (Italy or others), Gender (male vs females), ECOG PS (0-1 vs 2), Histology

---	--

 
Sistema Socio Sanitario Regione Lombardia
		OBSERVATIONAL STUDY PROTOCOL	MOD-PRO-G-03- DSC-10
---	---	---	---------------------------------

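### The primary endpoint is the act of building a model, which is met at any accuracy, and it does not match the stated primary objective, the powered comparison or the success rule

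*Protocol*

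**What the plan says.** All references are to the protocol.

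- **Study Endpoints, primary:** the entry reads "The predictive model will be developed through artificial intelligence and machine learning analysis of the integrated clinical, biological, genomics, metabolomics, circulomics, pathomics, microbiome", with radiomics completing the list. There is no other primary endpoint.
- **Overall Primary Objective:** the stated aim is "Prediction of response to immune checkpoint inhibitors in NSCLC by using clinical, biological, metabolomics, genomics, pathomics and radiomics data".
- **Secondary Objectives:** one of the entries is "Prediction of Objective Response Rate (ORR) in response to immune checkpoint inhibitors in NSCLC by using clinical, biological, metabolomics, genomics, circulomics, pathomics, microbiome", with radiomics completing the list. PFS and OS have parallel entries.
- **Study Endpoints, secondary:** one of the entries is "Prediction of Objective response rate (ORR) classification through the predictive model and compared to the assessed by the investigator", defined by confirmed CR or PR under RECIST v1.1. This is the only place where response is an endpoint.
- **Specific Objectives, Prospective Study Phase:** the aim is given as "The primary objective of the prospective phases to compare the predictive accuracy of ML methods" with validated biomarkers, PD-L1 being the example. The outcome to be predicted is not given.
- **Sample size and statistical analysis:** the primary objective is again accuracy of ML methods compared "with current validated biomarkers (e.g., PD-L1 or available scores, see Table 2"). It is powered at 85% or more for an AUC gain of 0.1 over 0.6, one-sided 0.05, 200 prospective cases. The outcome behind the AUC is not named.
- **AI analysis plan:** the phase counts as successful if the P-Model beats current biomarkers by at least 10% on 2-year PFS and OS, measured with Harrell's C.

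**The concern.** A primary endpoint should be a quantity measured on patients that can come out for or against the claim. This one is reached when a model exists, even one that predicts no better than chance. A statistical analysis plan cannot repair that by adding detail, because the protocol has fixed as primary something that has no value to estimate.

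A reader who looks elsewhere for the real target finds three candidates: response, an AUC for an unnamed outcome, and 2-year PFS or OS by a C statistic. The documents do not say which one carries the primary claim. Nor do they say whether the primary model includes circulomics and microbiome. That leaves outcome, metric and input set open to choice after results are seen. The consequence matters because the tool is meant to guide treatment choice, and the protocol plans preliminary work towards CE marking.

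**Working it through.** **1. The sections side by side**

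| Section | Outcome | Metric | Comparator | Threshold |
|---|---|---|---|---|
| Primary endpoint | none | none | none | none |
| Overall Primary Objective | response, undefined | none | none | none |
| Secondary endpoint | ORR, RECIST v1.1 | classification | investigator assessment | none |
| Prospective phase objective | none | predictive accuracy | biomarkers, e.g. PD-L1 | none |
| Sample size | none | AUC | PD-L1 or available scores | +0.1 over 0.6 |
| AI analysis plan | 2-year PFS, 2-year OS | Harrell's C | current biomarkers | at least 10% better |

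No row ties response to a primary test. The powered row has no outcome, and the success row has different outcomes and a different metric from every other row. The sample-size remark that the data are discrete rating-scale responses describes the type of score entering the ROC curve; it does not name tumour response as the outcome.

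**2. Inputs**

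Primary objective, six types: clinical, biological, metabolomics, genomics, pathomics, radiomics. Primary endpoint, eight types: the same six plus circulomics and microbiome. The secondary objectives also list all eight. The data table in Methodology and study design marks circulating and microbiome data as prospective only, so the eight-type list can apply only to the prospective model.

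**3. Can the stated power be reproduced?**

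Inputs from the sample-size section: N = 200, AUC 0.60 against 0.70, one-sided alpha 0.05 (z = 1.645). Two further inputs are needed and not given: the share of patients with the outcome and the correlation r between the two AUC estimates. Both are varied here as assumptions.

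Hanley-McNeil variance of an AUC, with n1 patients having the outcome and n0 not:

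V(A) = [A(1−A) + (n1−1)(Q1−A²) + (n0−1)(Q2−A²)] / (n1·n0), where Q1 = A/(2−A) and Q2 = 2A²/(1+A).

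- A = 0.60: Q1 = 0.4286, Q2 = 0.4500.
- A = 0.70: Q1 = 0.5385, Q2 = 0.5765.

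SE = √(V0 + V1 − 2r√(V0·V1)); power = Φ(0.10/SE − 1.645).

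- 50% share (100/100), r = 0.5: V0 = 0.001594, V1 = 0.001357, SE = 0.0385. Power = Φ(0.954) = 83%.
- 30% share (60/140), r = 0.5: V0 = 0.001999, V1 = 0.001796, SE = 0.0436. Power = Φ(0.649) = 74%.

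| Outcome share | r = 0 | r = 0.3 | r = 0.5 | r = 0.6 | r needed for 85% |
|---|---|---|---|---|---|
| 50% | 58% | 71% | 83% | 90% | 0.53 |
| 30% | 49% | 62% | 74% | 82% | 0.63 |
| 20% | 40% | 51% | 63% | 71% | 0.73 |

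The binormal rating-scale variance formula gives values within about two percentage points. The stated 85% is therefore attainable under some assumptions and not under others. It can be neither confirmed nor refuted until the outcome, and hence its share, is named.

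**The case against.** The strongest reply is that the protocol does hold falsifiable comparisons. Specific Objectives, Scientific Clinical Study Design and the sample-size section all give accuracy against validated biomarkers as the main or primary aim. The sample-size section powers it, and the AI analysis plan adds a success rule that the model could fail. This stands. A reader might infer from the primary endpoint that the study can claim success with no evidence of accuracy; these sections do not support that. What remains is that the formal primary endpoint is none of these, and that they disagree among themselves.

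The reply also notes that the protocol uses response loosely, writing of PFS and OS in response to treatment. The primary objective may therefore mean benefit in general, with ORR, PFS and OS as its measures. That is possible, so strict duplication between the primary objective and secondary ORR is not established. The ambiguity itself needs settling.

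Two further inferences should not be drawn:

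- One might calculate an inflated false-positive rate from testing several outcomes and input sets. The protocol specifies one test at one-sided 0.05 and no correlations, so such a figure would rest on tests it does not plan.
- The comparator reference to Table 2, read with "the following multi-OMICs data will be collected for all 200 patients with available tissue and blood. For details see Table 2", might suggest that the study's own assays are the comparators. No table captions survive in the text at hand, so the numbering cannot be verified, and PD-L1 is repeatedly the named example.

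**Conclusion.** The point holds as a fault of definition and alignment. The primary endpoint has no measurable content and is met at any accuracy. It does not agree with the primary objective, the powered comparison or the success rule, and its input list exceeds the primary objective's by circulomics and microbiome. These findings rest on the wording alone.

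The numerical consequence is conditional. At an assumed correlation of 0.5, neither a 50% nor a 30% outcome share reaches the stated 85%, so that figure may need lowering once the outcome is chosen. It is not shown to be wrong, since a higher correlation would reach it.

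**What to change.** 1. Replace the primary endpoint with the quantity the study is powered on: the difference in AUC between the ML index and PD-L1 in the prospective cohort, for one named binary outcome.
2. Choose that outcome explicitly. Confirmed CR/PR by RECIST v1.1 is the natural choice if response in the primary objective is meant literally; ORR would then leave the secondary list, and the protocol should say how it applies to patients on consolidation treatment. Otherwise use a 2-year landmark of PFS or OS; since the planned minimum follow-up is 18 months, patients censored before 24 months would need a stated handling.
3. Carry the same outcome, metric and comparator through the Overall Primary Objective, Specific Objectives, Study Endpoints, sample-size section and AI analysis plan. Make the PFS/OS C-statistic rule secondary or bring it into line. Name any other scores as secondary comparators.
4. Use one input list, the eight types in the primary endpoint, for the prospective model in both objective and endpoint.
5. Restate the power for the chosen outcome, giving the assumed outcome share and between-score correlation.

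Cost: wording changes in several sections and possibly a less favourable stated power. No new data items are needed, since PD-L1, best response to first line, PFS and OS are already collected.

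### The PFS and OS secondary endpoints are defined through classes of the model index, which costs information that a continuous analysis would keep and does not match the concordance measure used to judge success

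*Protocol*

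**What the plan says.** Protocol, Study Endpoints, gives two time-to-event secondary endpoints.

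- PFS: "Using the predictive model index as classificatory biomarker in Progression-free survival (PFS", with the analysis described as "whichever occurs first and calculated through censored Kaplan-Meier analysis".
- OS: "Using the predictive model index as classificatory biomarker in Overall survival (OS) calculated from diagnosis to death or last follow-up", again by censored Kaplan-Meier.

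No number of classes, cut, source of a cut, test or significance level is given for either.

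Protocol, AI analysis plan, treats the same two outcomes differently. The phase succeeds if the P-Model "outperforms current biomarkers prediction at least for 10% in terms of correct prediction", and the yardstick is "correct prediction of either 2-year PFS and 2-year OS, measured with" Harrell's C. The final comparison comes "after the predictive models are build using all the data from 200 patients".

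The only power statement, under Sample size and statistical analysis, concerns an AUC gain. It opens with "Considering the number of 200 prospective cases" and does not cover PFS or OS.

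**The concern.** A Kaplan-Meier analysis by index can only be drawn for groups, so the endpoint wording commits the protocol to cutting the index. If the model returns a continuous score, patients within a class are then treated as alike and the result depends on where the cut falls. Separation between classes is also a different quantity from concordance, so the secondary endpoints would not describe the measure on which success is judged.

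Two things are at stake: power to show that the index relates to PFS and OS in a cohort of only 200, and the credibility of the curves. Under Clinical relevance, the protocol intends the tool to help select candidates for immunotherapy. Two well-separated curves would carry weight there, so it matters that no cut is tuned to produce them.

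**Working it through.** **Plan's own figure.** None exists for PFS or OS. The stated power of at least 85% is for an AUC of 0.7 against 0.6 (one-sided 0.05). With a 100:100 outcome split and a rating-scale variance it is about 56%, 82% and 89% at correlations of 0, 0.5 and 0.6 between the two AUCs. It is attainable, but it says nothing about the class-based survival analyses.

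**Inputs.** From the protocol: 200 prospective patients. Assumed, because the protocol does not give them: a normal continuous index, the hazard ratio per SD, the number of events, and a two-sided 5% level.

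**Step 1: information kept.** For one cut at quantile p, the share kept is φ(z_p)² / [p(1−p)]. At the median this is 0.3989² / 0.25 = 2/π = 0.637, a loss of 36.3%. For k equal classes, the share kept is the mean of the squared class means of a standard normal variable.

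| Grouping | Kept | Lost |
|---|---|---|
| 2 classes, median | 63.7% | 36.3% |
| 2 classes, 30/70 | 57.6% | 42.4% |
| 2 classes, 20/80 | 49.0% | 51.0% |
| 3 equal classes | 79.3% | 20.7% |
| 4 equal classes | 86.1% | 13.9% |
| 5 equal classes | 89.7% | 10.3% |

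**Step 2: power.** Power = Φ(√(d × share kept) × ln HR − 1.96), with d events. For HR 1.3 per SD, ln HR = 0.262. At d = 120:

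- continuous: √120 × 0.262 − 1.96 = 0.91, power 0.82;
- median split: √(120 × 0.637) × 0.262 − 1.96 = 0.33, power 0.63.

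| HR per SD | Events | Continuous | Median split |
|---|---|---|---|
| 1.2 | 120 | 0.52 | 0.36 |
| 1.3 | 100 | 0.75 | 0.55 |
| 1.3 | 120 | 0.82 | 0.63 |
| 1.3 | 150 | 0.90 | 0.73 |
| 1.4 | 120 | 0.96 | 0.84 |

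**Step 3: false positives, conditional on a searched cut.** Null data were simulated for 200 patients with exponential survival and uniform censoring. The cut with the largest log-rank statistic was tested at nominal two-sided 5%.

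- 41 candidate cuts between the 10th and 90th percentiles (2,000 data sets): 38%.
- Every cut in the same range (4,000 data sets, about 157 events): 45%. The Miller–Siegmund approximation gives 49%.
- Every cut in the inner 50%: 29%. In the inner 90%: 52%.
- Cut preset at the median: about 5% (4.5% to 5.3% across runs).

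**Step 4: where a cut could come from.** The baseline data table under Methodology and study design ticks immunohistochemistry, circulating immune cells, cytokines and microRNA, cell-free DNA, genomics, metabolomics and microbiome for the prospective phase only. The full multi-omics index therefore cannot be computed in the roughly 2,000 retrospective patients. They can supply a cut for the R-Model index only.

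**The case against.** The strongest reply is that the information is not lost to the study. Harrell's C is already the success measure for PFS and OS and can use the uncut index, although the protocol does not say that it will. Curves by class are a reasonable complement, since selecting patients is itself a classification. This stands as far as the success criterion goes. It does not rescue the endpoint wording, which names only the class-based analysis.

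The 36% also depends on choices the protocol does not make. More classes lose less, and the index is nowhere said to be continuous or normal; the AUC calculation even assumes rating-scale data. That stands too, so the loss is given as a range with its conditions.

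A reader might infer that the cut will be searched for in the 200 prospective patients and that PFS and OS therefore carry a false-positive rate near 40%. The protocol does not support this. It describes no search, names no log-rank test and sets no significance level for these endpoints, and a cut rule may properly sit in a statistical analysis plan that is not shown. The final model is built on all 200 and the full index exists only for patients with omics data, so the risk is worth closing off. A quantile rule set in advance would still carry no inflation.

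**Conclusion.** The point holds as a choice of method. The protocol fixes a class-based Kaplan-Meier analysis for PFS and OS where a continuous analysis would be more powerful and would match its own concordance criterion.

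The loss is about 36% of the information for a median split of a normal index, and about 21%, 14% and 10% for three, four and five equal classes. At an assumed HR of 1.3 per SD and 120 events, this means power of 0.63 instead of 0.82 for the median split.

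The false-positive figure of 38–45% is a warning about one procedure that the protocol neither adopts nor excludes. It is not a property of the plan. The absence of a stated cut is not in itself an error.

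The endpoints are secondary, the primary AUC comparison is unaffected, and the change is cheap. It should be made, but it does not put the study in question.

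**What to change.** In Study Endpoints, restate the PFS and OS analyses of the index as continuous: a Cox hazard ratio per SD with a spline check of linearity, plus Harrell's C as in the AI analysis plan. Keep Kaplan-Meier curves by preset quantile groups, such as thirds, for display only.

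If a clinical cut is wanted, fix it before prospective outcomes are opened. For the R-Model index, set it in the retrospective cohort. For the multi-omics P-Model index, use a preset quantile rule, or choose the cut within cross-validation so that no patient is assessed with a cut that their own outcome helped to set.

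The cost is revised endpoint wording and slightly more analysis work, with no added patients, visits or samples. The one real drawback is that a hazard ratio per SD is less direct for clinicians than two curves, which the display curves largely offset.
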